- Hepatic function tests including alkaline phosphatase (ALP), aspartate aminotransferase (AST), alanine aminotransferase (ALT), gamma-glutamyl transferase (GGT), total and direct bilirubin to assess hepatic function and integrity;
- Plasma phytosterol (stigmasterol, campesterol, and sitosterol), cholesterol and squalene levels to determine potential correlation with the development of PNALD;
- Holman Index and fatty acid profiles will be evaluated. Select polymorphisms in the fatty acid desaturase genes, FADS1 and FADS2, will be determined in a subset of patients. The major plasma phytosterols found in the lipid emulsions (stigmasterol, campesterol, and sitosterol), cholesterol, and squalene also will be assessed.

After end of study treatment (maximum of 90 days), the patient will resume PN therapy as prescribed by their healthcare provider.

Study Population:

Key Inclusion Criteria:

- 1. Patients who are expected to require PN for at least 7 days;
- Premature infants (born at 24 to <37 weeks of gestation with a birth weight ≥750 g) must require at least 80% of targeted energy requirements by PN at study entry (up to 1 month CA); full term infants and children must require at least 70% of targeted energy requirements by PN at entry into the study;
- 3. A patient, or legal representative, has signed a written informed consent form per 21 CFR Part 50.55(e).

Key Exclusion Criteria:

- 1. Patients who are not expected to survive hospitalization or with a severe critical unresponsive illness at time of initiation with foreseeable intercurrent events that could jeopardize the patient's participation in the study (i.e. unresponsive shock, sepsis, renal failure requiring dialysis, severe unresponsive metabolic acidosis, and/or severe unresponsive metabolic disorders), as judged by the Investigator;
- 2. Patients with a known hypersensitivity to lipid emulsion, egg or soybean proteins, or any of the active substances, excipients, or components of the container or who have a history of an adverse event due to ILE;

- 3. Patients with liver disease including cholestasis;
- 4. Patients with severe hyperlipidemia or severe disorders of lipid metabolism characterized by hypertriglyceridemia (i.e. triglyceride >400 mg/dL);
- 5. Premature infants born <24 weeks of gestation and patients ≥ 18 years;
- 6. Patient requires or is expected to require propofol for sedation;

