- Hepatic integrity (ALP, AST, ALT, GGT, total and direct bilirubin) will be evaluated by presenting descriptive summary statistics of individual values at different measurement time points from baseline to end of study treatment during the study period in each of the 2 treatment groups. Hepatic integrity parameters will also be summarized in shift tables comparing results from baseline to end of study treatment (max 90 days) and to maximal value during the study period in each of the 2 treatment groups. In addition, assessment for drug-induced liver injury will be conducted according to Hy's Law and eDISH criteria.^{1,2}
- 2. Adequacy of nutritional intervention

The adequacy of nutritional intervention in patients receiving either Clinolipid or Intralipid will be assessed and results analyzed as follows:

- Prescribed and actual nutritional intakes (calories, protein, lipids and carbohydrates) from both PN and enteral/oral nutrition will be collected and recorded on a daily basis and summarized daily for the first 2 weeks of treatment and on an approximately every 15-day basis afterwards up to the end of study treatment in each of the treatment groups.
- Growth will be assessed and evaluated from baseline to end of study treatment on an approximately every 15-day basis using descriptive summary statistics for weight, and height/length (and head circumference in infants <1 year) in each of the treatment groups as follows:
- Gain in weight (g/kg/day in infants and g/day in children and adolescents), and gain in length/height (mm/week in all) and head circumference (mm/week in infants <1 year);
- Changes in the standard deviation score (SDS or z-score) from reference growth curves (Fenton growth curve for premature infants, World Health Organization growth standards for infants and children ages 0 to 2 years, or Center for Disease Control growth charts for children age ≥2 years).
- 3. Safety profiles of Clinolipid and Intralipid, including AEs, SAEs and AESIs.

The safety profiles will be assessed and analyzed as follows:

- Vital signs and laboratory tests will be summarized using descriptive summary statistics in each of the 2 treatment groups.
- Additional neonatal morbidities including bronchopulmonary dysplasia (BPD), retinopathy of prematurity (ROP), intraventricular hemorrhage (IVH), periventricular leukomalacia (PVL), necrotizing enterocolitis (NEC), and late-onset sepsis in enrolled premature infants born <37 weeks of gestation up to 1 month CA.

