5. STUDY TREATMENT(S)

5.1 Description of Treatment(s) and Dosing

The PN guidelines for the provision of macronutrient in infants, children, and adolescents are provided in Table 3.

Micronutrients (electrolytes, minerals, trace elements and vitamins) should also be included in PN regimen based upon patient needs.

	Energy (kcal/kg/d)	Amino acids (g/kg/d)	Glucose (g/kg/d)		Lipids (g/kg/d)	
	Target	Target	Start	Target	Start	Target
Preterm infants (<37wks)	90-120	3-4	6-8	10-14 (max.18)	0.5-1	3 (max.4)
Term infants (0-1y)	90-100	2.5-3	6-8	10-14 (max.18)	0.5-1	2.5-3 (max.3)
Children (1-10y)	55-80	1-2.5	3-6	8-10	1-2	2-3 (max.3)
Adolescents (10-18y)	30-55	0.8-2	2.5-3	5-6	1	1-2 (max.3)

Table 3. General Pediatric Parenteral Nutrition Guidelines

Adapted from AAP 2014,¹⁹ ASPEN 2015,²⁰ and ESPGHAN/ESPEN/ESPR/CSPEN 2018^{21,22}

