2. ANALYSIS METHODS

2.1 General Principles

Unless otherwise specified, summary statistics (n, mean, standard deviation [SD], median, minimum, and maximum values) will be presented for continuous variables. Counts and, if relevant, percentages will be presented for categorical variables.

Unless otherwise specified, data listings will include patient ID, treatment group, sex, age at screening (given in months) and baseline weight.

Unless otherwise noted, all analyses will be performed using SAS/Graph® 9.4 software, SAS/STAT® 15.1 software, and Base SAS® 9.4. Copyright © 2016, SAS Institute Inc. SAS and all other SAS Institute Inc. product or service names are registered trademarks or trademarks of SAS Institute Inc., Cary, NC, USA. All Rights Reserved

Except for height, weight, head circumference, or otherwise specified, the estimated mean, Q1, median, and Q3 for a set of values will be displayed to 1 more significant digit than the original values, standard deviations will be displayed to 2 more significant digits, and minimum and maximum values will be displayed with the same number of significant digits as the original values. If an original value has more than 2 decimal places, the significant digits will be counted as if there are 2 decimal places. All percentages will be displayed with 1 decimal place unless more decimal places are needed to show 1 significant digit (i.e. a percentage of 0.01 will be shown as 0.01 as opposed to 0.0). For height, weight, and head circumference, up to 4 reported decimals are shown.

Unless otherwise specified, age group will be defined and stratified as follows: Pre-Term Neonate (24 weeks to <37 weeks), Full Term Neonate (\geq 37 weeks to <1 month), Infant (\geq 1 month to <12 months), Child (\geq 1 year to <10 years), and Adolescent (\geq 10 years to <18 years)

Unless otherwise specified, weight at birth will be grouped as follows: Normal (\geq 2500 g), Low (1500-2499 g), Very Low (1000-1499 g), and Extremely Low (<1000 g).

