2.1.2 Visit Windows

The study visits can be obtained from the eCRF and need not be derived programmatically. The visits will be displayed as: Screening, Day 1 (Baseline), Day 2, ... Day 14, Day 15, Day 30, Day 45, Day 60, Day 75, Day 90/End of treatment (EOT).

Results from unscheduled visits will not be included in table summaries. These values will only be presented in the listings.

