2.4.3 Adequacy of Nutritional Interventions

Prescribed (ordered) and actual (administered) nutritional intake (fluid, energy, protein, carbohydrates, and lipids) from parenteral, enteral nutrition, and IV fluids will be collected and recorded daily. They will be summarized descriptively on a daily basis during the first 2 weeks of treatment and on a 15-day basis afterwards up to end of study treatment for each of the treatment groups. Summaries of overall nutritional intake will also be done. Box plots will also be produced by day and treatment group.

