2.4.3.1 Parenteral Nutritional Intake

Data from parental nutrition will be calculated as follows:

Fluid intake ordered (mL/kg/24 hours):

24 * Total volume ordered(mL) PN dosing weight (kg) Total PN Infusion Duration (hours)

Fluid intake administered (mL/kg/24 hours):

24 * Total volume administered(mL) PN dosing weight (kg) Total PN Infusion Duration (hours)

Energy intake ordered (kCal/kg/24 hours):

Total calories (kCal) should first be calculated as³:

Protein intake (g/kg) *PN dosing Weight (kg) * 4 + Lipid intake (g/kg) * lipid dosing weight (kg) * 10 + $\frac{Carbohydrate intake (g/dL)}{100}$ * Fluid intake ordered (mL/kg) * PN dosing Weight(kg)*3.4 Then energy intake can be calculated as:

> 24 * Total calories (kCal) PN dosing Weight (kg) Total PN Infusion Duration (hours)

Energy intake administered (kCal/kg/24 hours):

Total Volume Administered
Total Volume Ordered* Energy Intake Ordered

Protein intake ordered (g/kg/24 hours):

24 * Protein intake (g/kg) Total PN Infusion Duration (hours)

Protein intake administered (g/kg/24 hours):

Total Volume AdministeredTotal Volume Ordered* Protein Intake Ordered

Carbohydrate intake ordered (g/kg/24 hours):

Dextrose intake (g/dL) * Total volume ordered (mL)24 *100 * PN dosing weight (kg)Total PN Infusion Duration (hours)

Carbohydrate intake administered (g/kg/24 hours):

Total Volume AdministeredTotal Volume Ordered* Carbohydrate Intake Ordered

Lipid intake ordered (g/kg/24 hours):

 $\frac{24 * \frac{0.2(\frac{g}{mL}) * Total \ lipid \ volume \ ordered \ (mL)}{Lipid \ dosing \ weight \ (kg)}}{Total \ Lipid \ Infusion \ Duration \ (hours)}$

Lipid intake administered (g/kg/24 hours):

$$\frac{24 * \frac{0.2 \left(\frac{g}{mL}\right) * \text{ Total lipid volume administered (mL)}}{\text{Lipid dosing weight (kg)}}}{\text{Total Lipid Infusion Duration (hours)}}$$

If lipid dosing weight is missing, PN dosing weight will be used instead. If both are missing, the recorded weight on the closest, prior non-missing day will be used.

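### The SAP's intake tables are per-kg summaries by arm only, with no age split and no comparison with the age-specific targets, so on their own they do not show whether intake was adequate

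*Protocol*

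**What the plan says.** The protocol synopsis has daily prescribed and actual intakes "summarized daily for the first 2 weeks of treatment and on an approximately every 15-day basis afterwards". SAP 2.4.3 repeats this: "They will be summarized descriptively on a daily basis during the first 2 weeks of treatment and on a 15-day basis afterwards". The SAP's formulas express intake per kg per 24 hours. The general rule in SAP 2.1 is that "summary statistics (n, mean, standard deviation [SD], median, minimum, and maximum values) will be presented for continuous variables", and SAP 2.4.3 adds that "Box plots will also be produced by day and treatment group". The four intake tables in the SAP's appendix (14.3.6.4.1 to 14.3.6.4.4) are listed for the FAS, and none has an age-group version.

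The yardsticks are in the protocol. Section 5.1 contains Table 3, "General Pediatric Parenteral Nutrition Guidelines", with targets by age class. Eligibility already uses a target: premature infants "must require at least 80% of targeted energy requirements by PN at study entry", and the figure is 70% for full-term infants and children. Protocol 5.7 promises a tabulation of reasons for not meeting standard-of-care targets. Protocol 9.3 promises subgroup analyses by the five age groups. SAP section 3 declares no changes from the protocol.

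For the later time points, the visit list in SAP 2.1.2 runs "Day 14, Day 15, Day 30, Day 45, Day 60, Day 75, Day 90/End of treatment (EOT", with visits taken from the eCRF rather than derived.

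**The concern.** The endpoint is called adequacy, but SAP 2.4.3 defines no comparison that would show it. It has no threshold, no percentage of target and no count of patients reaching a target. The protocol's age subgroups are not carried into the intake outputs, and the tabulation promised in protocol 5.7 has no table in the SAP's list.

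Age is what gives a per-kg figure its meaning here. If preterm infants and adolescents share one summary, a reader cannot tell who was fed to target. This also bears on the primary endpoint, because the study is described as concerning patients who were adequately treated, and EFAD rates are harder to interpret if intake adequacy is unknown.

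The timing rule is a smaller, related gap. Intake is recorded every day, but the SAP does not say how the days between the 15-day visits enter the tables.

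**Working it through.** There is no plan figure to reproduce. The sample size of 100 rests on feasibility and the endpoint is descriptive, so no power formula applies.

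**1. Spread of the targets (protocol Table 3, energy in kcal/kg/day)**

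| Age class | Target | Midpoint |
|---|---|---|
| Preterm | 90-120 | 105 |
| Term, 0-1 y | 90-100 | 95 |
| Children | 55-80 | 67.5 |
| Adolescents | 30-55 | 42.5 |

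Preterm against adolescent: 90/30 = 3.0 at the lower bounds and 120/55 = 2.2 at the upper bounds. A value of 60 is inside the children's range, above the adolescents' range, and 60/90 = 67% of the lower bound for infants.

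**2. What a pooled mean does.** Pooled mean = sum of (patients in class × class midpoint × fraction of target received) / 50. The age mixes of a 50-patient arm are assumptions.

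| Assumed mix (preterm/term/child/adolescent) | All at midpoint | Infants at 80%, older patients at 130% |
|---|---|---|
| 40/8/1/1 | 101.4 | 82.2 |
| 25/15/6/4 | 92.5 | 79.8 |
| 20/10/10/10 | 83.0 | 77.4 |
| 10/10/15/15 | 73.0 | 74.9 |

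- Last row, fully fed: (10×105 + 10×95 + 15×67.5 + 15×42.5)/50 = 3650/50 = 73.0.
- Last row, infants underfed: (0.8×2000 + 1.3×1650)/50 = 3745/50 = 74.9. The underfeeding is hidden.
- First two rows: the mean falls by 19.2 and 12.7, so the underfeeding shows.
- Everyone at 75% of target in the 40/8/1/1 mix: 0.75×101.4 = 76.05, which is above the fully fed 10/10/15/15 mix.

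On a percentage-of-own-target scale, everyone at target reads 100% and everyone at 75% reads 75%, whatever the mix.

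**3. Is age stratification implied elsewhere?** SAP 2.1 defines the age groups. SAP 2.3.1 and 2.3.5 then state age-group presentation explicitly for demographics and baseline measurements. SAP 2.4.3, its box plots and its tables state treatment group only.

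**4. The 15-day basis.** Pointing to visit-day values: the visit list in SAP 2.1.2, the per-patient-per-day totals in 2.4.3.4, and the absence of any averaging formula. By contrast, SAP 2.4.3.5 defines growth over the last 15 days. Under the visit-day reading, 6 of the 76 days from Day 15 to Day 90 (7.9%) reach a table, or 20 of 90 days (22%) overall. Under the interval reading, all days count.

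The variance of a 15-day mean relative to one day is r + (1−r)/15, where r is the assumed within-patient day-to-day correlation. For r = 0.3, 0.5 and 0.7 this gives 0.35, 0.53 and 0.72, so the variance is 28% to 65% lower.

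**5. Scaling that affects any percentage of target.** The PN formulas in SAP 2.4.3.1 multiply by 24/infusion duration. For a 20-hour infusion, 24/20 = 1.2, so 3 g/kg actually given is reported as 3.6.

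**The case against.** Several things weigh against a stronger statement.

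- A reader might infer that the study intends to ignore age. It does not. Protocol 9.3 plans age-subgroup analyses without limiting them to one endpoint. What stands is that the SAP does not carry them into the intake outputs.
- A reader might infer that only means are reported. The SAP also gives medians, minima, maxima and box plots. These show spread, but a pooled distribution still does not say which patients are below their own target.
- A reader might infer that adequacy cannot be judged at all. Growth is the other half of the endpoint, and SDS change is measured against age-appropriate reference curves. Ordered and administered intake are both summarised, and listings exist. Growth is an outcome of feeding, however, and does not measure intake.
- A reader might take single visit-day reporting after Day 15 as stated. It is the better-supported reading, but no text says so, and the day counts and variance figures above depend on it.
- A reader might argue that visit days are atypical because of the 4-hour lipid hold before fatty-acid sampling. Protocol 6.7.2.4 lets other PN components continue, 20-hour infusion is already normal, and SAP 2.4.3.1 rescales lipid by infusion duration. The documents do not show that the reported values would be distorted.
- Masking is not inevitable, as the infant-heavy mixes show. Randomisation stratified by age also limits imbalance between arms at entry, though not changes in mix as patients leave PN.

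Finally, this is a secondary endpoint in a descriptive study without formal testing, which limits the consequence.

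**Conclusion.** The point holds in this form: followed as written, the SAP's intake tables and plots do not by themselves show whether patients were fed to target. They omit the protocol's age subgroups without declaring a change, and they never use the age-specific targets that the protocol supplies. Targets differ about two- to threefold by age. In the examples, infants at 80% of target ranged from fully hidden (74.9 against 73.0) to plainly visible (82.2 against 101.4). Those figures rest on assumed mixes and Table 3 midpoints, and the documents give no planned age mix, so the actual degree of masking is unknown.

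The timing rule is an ambiguity to settle, not a demonstrated loss of data. The documents support a gap in specification that the SAP can close, not a claim that the endpoint is beyond evaluation. It should be amended.

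**What to change.** Amend SAP 2.4.3 as follows.

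1. Report intake by arm within age group, as protocol 9.3 already provides. Add administered energy from all sources as a percentage of the Table 3 target for the patient's age class (full-term neonates and infants share the 0-1 year row). Give the mean percentage and the n (%) at or above the lower target. Label it a benchmark, because Table 3 is a PN guideline.
2. Do the same for protein from PN and measured enteral sources. State that protein from oral food is not recorded (protocol 6.9). SAP 2.4.3.4 currently totals only fluid and energy, so a protein total must be added.
3. Compute the percentages from the amounts actually given each day, not from values scaled by 24/infusion duration. SAP 2.5.2.6 already does this for the administered lipid dose.
4. After Day 15, summarise each patient's mean daily intake over the interval (Days 16-30, 31-45, and so on), with the last interval ending on the last full PN day.

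The cost is SAP wording and some extra programming on daily data that are largely collected already; no study procedure changes. The downsides are small numbers in some age groups and a benchmark that is not an individual prescription.

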EPA	eicosapentaenoic acid
FA(s)	fatty acid(s)
FAS	full analysis set
FADS1	fatty acid desaturase 1 gene
FADS2	fatty acid desaturase 2 gene
GA	gestational age
GCP	Good Clinical Practice
GGT	gamma glutamyl transferase
GI	gastrointestinal
hCG	human chorionic gonadotropin
IC	informed consent
ICF	informed consent form
ICH	International Council for Harmonisation
ILE	intravenous lipid emulsion
IP	investigational product
IRB	Institutional Review Board

IVH	intraventricular hemorrhage
LA	linoleic acid
MedDRA	Medical Dictionary for Regulatory Activities
NEC	necrotizing enterocolitis
00	Olive oil
PN	parenteral nutrition
PNALD	parenteral nutrition-associated liver disease
PPS	per protocol set
PUFA	polyunsaturated fatty acid
PVL	periventricular leukomalacia
ROP	retinopathy of prematurity
SAE	serious adverse event
SAP	statistical analysis plan
SDS	standard deviation score
SNP	single nucleotide polymorphism
SO	soybean oil
SOC	standard of care
USP	United States Pharmacopeia
USPI	United States Prescribing Information
WHO	World Health Organization

_

1. INTRODUCTION

Although humans and other mammals can easily synthesize most fatty acids (FAs) from carbon groups in carbohydrates and proteins, they lack the desaturase enzymes necessary to insert a cis double bond at the n-6 and n-3 positions of a FA. As a result, the parent polyunsaturated fatty acid (PUFA) of the n-6 series, linoleic acid (LA, 18:2n-6), and the parent PUFA of the n-3 series, alpha-linolenic acid (ALA, 18:3n-3), are considered essential and indispensable for the synthesis of other long chain PUFAs of the n-6 and n-3 series.

It is currently estimated that essential fatty acid deficiency (EFAD) may occur in human when LA and ALA intake is less than 2-4% and 0.25-0.5% of energy intakes, respectively.³ The clinical manifestations of EFAD are a flaky dry skin, hair loss, hair depigmentation, poor wound healing, increased susceptibility to infections, and poor growth in infants and children.³ Biochemical characteristics include decreased blood and tissue PUFAs from the n-6 and n-3 series and an elevated triene:tetraene ratio (T:T, Holman Index). Other biochemical manifestations of EFAD are considered non-specific and can include elevated liver enzymes, hyperlipidemia, thrombocytopenia and altered platelet aggregation.^{3,4}

EFAD is rare under usual circumstances in healthy humans who have access to a varied diet or have sufficient adipose tissue that allows fat store mobilization to prevent EFAD when exogenous supply is limited.^{3,4} Thus, EFAD primarily occurs in clinical circumstances that severely limit fat intake, digestion, absorption and metabolism and in the setting of severely depleted fat stores. Due to their high requirements and limited fat stores, young infants are at increased risk for EFAD, especially premature infants.^{4,5}

Parenteral nutrition (PN) is indicated for the supply of energy and essential nutrients when oral or enteral nutrition is not possible, insufficient, or contraindicated. Parenteral nutrition is essential for nutrient delivery in patients with gastrointestinal (GI) dysfunction who lack the capacity to absorb adequate nutrients for maintenance or recovery of tissue mass and function.

Intravenous lipid emulsions (ILEs) were developed in order to prevent and treat EFAD in patients who require PN, as well as to provide a high-density energy source. The first intravenous fat preparation used to any great extent in the United States was made from cottonseed oil and marketed under the tradename of Lipomul® and was withdrawn from the market in 1965 because of numerous reports of toxicity, including "the fat-overloading syndrome", hemorrhagic tendencies, and liver damage. The toxic accumulation of fat observed with Lipomul was attributed to its large particle size (1 nm

in diameter), and possibly the emulsifying agent, pluronic F-68.⁶ Subsequently, for several years PN did not include the provision of any lipid and was associated with several reports of EFAD.⁷⁻⁹

The post-Lipomul ILEs were developed from soybean oil (SO) or safflower oil, both rich in LA and ALA. SO contains about 45–55 % LA, 6–9 % ALA, and very little saturated or monounsaturated FAs. Intralipid, a 100% SO based ILE, was invented by the Swedish physician and nutrition researcher Arvid Wretlind, and was approved for clinical use in Sweden in 1962 and 10 years later in the United States.

Experimental and clinical research suggests that these purely SO-based ILEs may exert an oxidative stress, may have a negative influence on immunological functions, and may play a role in PN-associated liver disease (PNALD). These findings were felt to be related to its absolute high PUFA content, favoring lipid peroxidation, and the relative excess of n-6 PUFAs, favoring pro-inflammatory effects.^{10,11}

Several new ILEs were subsequently developed including other sources of FAs designed to decrease the proportion of SO. In addition to the classic 100% SO ILEs, new generation composite ILEs contained other lipids including medium chain triglycerides derived from coconut oil or other tropical nut oils, olive oil (OO), or fish oil, or a combination of several sources. These new generation ILEs potentially can provide advantages over pure SO ILEs and are widely available in Europe and Canada but not in the United States.^{4,5,12-14}

Clinolipid is an ILE comprised of a mixture of 80% OO and 20% SO. It was formulated with a lower SO content than currently marketed emulsions in order to reduce LA levels, while still providing an adequate amount of EFAs to prevent and correct EFAD in adult and pediatric patients requiring PN.¹⁵ This OO-based ILE is rich in oleic acid, an n-9 monounsaturated FA, that is considered immune neutral with potentially fewer adverse consequences on immunity compared to pure SO ILEs.¹⁰

Clinolipid has approximately one third of the LA content of a 100% SO ILE (fatty acid levels are provided in Table 1 and sterol composition is provided in Table 2). This reduction in the EFA supply could be a concern in a pediatric population, especially premature infants, who have higher EFA requirements than adults. Clinolipid has marketing authorization in approximately 50 countries. The current evidences of more than 20 years of clinical use suggest that Clinolipid is safe and can prevent EFAD.^{15,16} However, the objective of this study is to evaluate the risk of developing EFAD when using 20% Clinolipid in pediatric patients requiring PN compared to the use of a 100%

SO ILE (Intralipid 20%) that is still the standard-of-care (SOC) in current United States hospital settings.

Fatty Acid(s)	Intralipid 20%	Clinolipid 20%
Total Saturated Fatty Acids	15.6 %	16.6 %
Myristic acid (14:0)	0.1	0.0
Palmitic acid (16:0)	11.0	13.0
Stearic acid (18:0)	3.9	3.3
Total monounsaturated fatty acids	22.8 %	63.4 %
Palmitoleic acid (16:1n-7)	0.1	0.9
Oleic acid (18:1n-9)	20.9	59.7
Vaccenic acid (18:1n-7)	1.3	1.7
Gondoic acid (20:1n-9)	0.2	0.2
Total polyunsaturated fatty acids	61.7 %	20.0 %
Linoleic acid (18:2n-6)	54.7	18.6
γ-linolenic acid (18:3n-6)	ND	ND
α -linolenic acid (18:3n-3)	6.7	1.7
Arachidonic acid (20:4n-6)	0.2	0.2
EPA (20:5n-3)	ND	ND
DHA (22:6n-3)	0.1	0.1

Table 1. Fatty Acid Levels (mean levels) for Intralipid and Clinolipid

DHA = docosahexaenoic acid; EPA = eicosapentaenoic acid; ND = not detected; values represent mean % and are rounded to nearest tenth

Adapted from Harvey K et al.¹⁷

Sterols	Intralipid (Soybean Oil-Based)	Clinolipid (Olive Oil-based)
Squalene	7.43 ± 0.10	387.45 ± 2.30
Cholesterol	274.08 ± 3.55	109.70 ± 0.38
Campesterol	55.35 ± 0.48	13.33 ± 0.12
Stigmasterol	65.05 ± 0.52	12.15 ± 0.04
β-Sitosterol	302.64 ± 2.00	240.59 ± 2.08
β-Sitostanol	7.68 ± 0.25	4.57 ± 0.16
Lanosterol	8.35 ± 2.48	3.74 ± 0.20
Total sterols	713.15 ± 9.27	384.08 ± 2.98
Total phytosterols	439.07 ± 5.72	274.38 ± 2.60

Table 2. Sterol composition for Int	ralipid and Clinolipid (μg/mL ± SD)*
-------------------------------------	--------------------------------------

Sterols	Intralipid (Soybean Oil-Based)	Clinolipid (Olive Oil-based)
Phytosterols (mg) per 100 g of lipid	220 ± 2.86	137 ± 1.30

	Table 2. Stero	l composition fo	or Intralipid	and Clinolipid	$(\mu g/mL \pm SD)^*$
--	----------------	------------------	---------------	----------------	-----------------------

* All experiments were conducted in triplicate, and data are shown as mean \pm SD; lipid emulsions analyzed are representative of only a single Lot number. Adapted from Xu et al.¹⁸

